## 3.0 STUDY DESIGN

In this single-center pilot study, we will investigate possible short-term neurocognitive changes induced by deep brain stimulation (DBS) in patients with Parkinson’s disease between the “on” and off” state. During the “on” phase, bilateral monopolar stimulation of the electrode contact associated with the ventral STN will be turned on; testing in the “on” state will be tested at both theta (5-10 Hz) and gamma (100-180 Hz) stimulation. In order to improve blinding to “on” versus “off” states and increase the uniformity of stimulation parameters, the intensity will be adjusted to 2.5 V for all patients. Patients with baseline settings at less than 1.5 V will be excluded from the study. During the “off” phase, both DBS electrodes will be turned off. Since turning the stimulation “on” vs “off” may induce motor effects that could influence testing performance, we will examine if the order in which settings are applied impacts the results of cognitive testing.

During a single outpatient visit, a baseline assessment (baseline stimulation parameters, including frequency, pulse width and voltage) of each neuropsychological task will first be performed in order to accommodate patients to the given task and reduce practice effect. Patients will then perform a battery of tests with the stimulator “on” at the theta frequency, “on” at the gamma frequency, and off; the sequence of these three settings will be changed for each patient in a single-blind fashion. Thus, patients will complete this battery of tasks a total of four times. Duration of testing will be approximately three hours.

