The first task to be performed will be the RNGT, which evaluates executive functions such as updating and monitoring of information and inhibition of automatic responses. During this task, participants will be asked to say a sequence of 100 numbers (each number ranging from one to nine) as randomly as possible timed with an auditory pacing stimulus (1 kHz, 200 ms duration) at a rate of 1 Hz. Subjects will be instructed to listen to the first few pacing tones without responding. The loudness of the tone will be adjusted to a comfortable level for each individual. Randomness will be described as picking a piece of paper (numbered one through nine) out of a hat and subsequently replaced. We will analyze previously used measures to quantify deviation from randomness, including repetition measures (repetition of the same digit within a specific time frame), cycling measures (attempt to use all alternative digits before repeating a digit), and seriation measures (tendency to use natural order of numbers).

Executive functioning was also measured with the Delis Kaplan Executive Function System Color Word Interference Test (D-KEFS CWIT). The D-KEFS CWIT test consists of five subtests (verbal fluency, color naming, word reading, color-word interference, and color-word interference switching) subtests. For each subtest the total score consists of the total time in seconds to complete the test as well as the total number of commission and omission errors. The D-KEFS CWIT test has been suggested as a reliable and valid measure of the inhibition and switching aspect of executive functioning in patients with PD.

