The Quotient System will be used to measure hyperactivity, attention and impulsivity. It is a noninvasive device designed to capture micro movements of the head using an infrared motion detector in conjunction with a reflector worn on the test subject’s head while the patient completes a 15-20 minute computerized test. The device produces 4 measures of neurocognitive performance: motion analysis, attention analysis, shift in attention state and Quotient composite scores. These tasks are generally used to assess frontal lobe function. After the test is completed, patterns of motion, accuracy of the responses, and fluctuations in attention state are analyzed and scored using proprietary algorithms based on 19 or more parameters. The motion detection includes 6 movement metrics. The Attention Response Analysis includes measures of accuracy, omission errors, commission errors, latency, variability, and response time variability. Baseline movement data will be collected during “on” versus “off” stimulation to ensure that differences in tremor and/or dyskinesia does not

confound interpretation of hyperactivity, attention, or impulsivity. Data for each patient is compared to age and gender matched cohorts.

Data collected from the patients' medical charts will include age, gender, handedness, age at onset of epilepsy, highest level of education, primary language, language laterality, age at surgery, time from diagnosis to surgery medications, other medical conditions, imaging, symptoms, clinical rating scales for Parkinson's disease and previous neuropsychological scores.

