#### **6.0 STRATIFICATION/DESCRIPTIVE FACTORS/RANDOMIZATION SCHEME**

The order of stimulation parameters after baseline will be changed for each patient by moving the order by one step. E.g. patient 1: gamma, theta off; patient 2: theta, off, gamma; patient 3: off, gamma theta. The subject will not be told which setting is being used.

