#### **7.0 STUDY AGENT ADMINISTRATION OR INTERVENTION AND TOXICITY MANAGEMENT PLAN**

During the "on" phase, bilateral monopolar stimulation of the electrode contact associated with the ventral STN will be turned on; testing in the "on" state will be tested at both theta (5-10 Hz) and gamma (100-180 Hz) stimulation. In order to

improve blinding to “on” versus “off” states and increase the uniformity of stimulation parameters, the intensity will be adjusted to 2.5 V for all patients. During the “off” phase, both DBS electrodes will be turned off.

Parkinson’s disease patients routinely have their settings changed to optimize their therapy if they are not having adequate response to their current treatment, especially in their first few programming sessions. Patients also have a controller to turn it off and on. Stimulation is routinely turned off in clinic to check for symptoms, or by the patients, who have a controller. Many patients turn their stimulation off at night or for other reasons. The length of time (45 minutes) and adjustments that we are performing would only be for research. Theta stimulation is not routinely used clinically and would only be for research.

There are no risks of turning the stimulation off or lowering the frequency, but it is possible that during this they will not have the motor benefits of DBS (tremor, bradykinesia may return); however, once normal stimulation is turned back on this will resolve. Patients will be monitored during the testing and can stop participating at any point and we will return their stimulation settings back to baseline.

The CTSI Scientific Committee reviewed this study

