### 12.0 DATA COLLECTION AND MONITORING

RNGT, Verbal Fluency, D-KEFS CWIT task results will be de-identified using a key and collected on paper. They will be stored in a locked cupboard in a locked office. MRNs and the key will be kept on a password protected Excel 2016 (Microsoft) spreadsheet on an encrypted and secure computer. No one except the study personnel will have access to the spreadsheets or papers. The behavioral data collection process is built into the Quotient ADHD System, details of which are described on their website (<http://www.quotient-adhd.com>).

Data collected from patients electronic medical records will be coded and kept on a password protected Excel 2016 (Microsoft) spreadsheet on an encrypted and secure computer separate from the key. No one except the study personnel will have access to the spreadsheets or papers.

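### Only the patient is blinded: the plan does not keep the stimulation setting from whoever scores the paper-recorded tasks, and rotating the order cannot remove a scoring bias that follows the setting

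*Combined protocol and SAP*

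**What the plan says.** Section 3.0 declares the level of blinding: "the sequence of these three settings will be changed for each patient in a single-blind fashion". Section 6.0 names the one person from whom the setting is withheld: "The subject will not be told which setting is being used". The other blinding measure, a common voltage, is intended to "improve blinding to “on” versus “off” states and increase the uniformity of stimulation parameters" (Section 7.0); it is not aimed at the tester or scorer.

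The order is a fixed rule printed in the protocol: "The order of stimulation parameters after baseline will be changed for each patient by moving the order by one step" (Section 6.0).

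On recording, Section 12.0 says "RNGT, Verbal Fluency, D-KEFS CWIT task results will be de-identified using a key and collected on paper". It limits access to study personnel as a group and does not separate those who program, test and score. CWIT subtests are scored on "total time in seconds to complete the test as well as the total number of commission and omission errors" (Section 3.0). The Quotient differs: it is "scored using proprietary algorithms based on 19 or more parameters", and the power table in Section 13.0 marks it as exploratory. The three paper-recorded measures are the ones with projected sample sizes.

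Section 7.0 also notes that, with stimulation off or at a lower frequency, "tremor, bradykinesia may return".

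**The concern.** The background section states a directional hypothesis, that low-frequency stimulation will improve performance. If the person who decides whether a fluency word counts, or whether a CWIT response is an error, knows which setting produced the sheet, borderline calls can lean towards expectation. The key in Section 12.0 conceals who the patient is; nothing says that it conceals the setting.

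Both aims are within-patient contrasts between settings. A lean that depends on the setting adds directly to those contrasts, and the planned within-subjects analysis cannot tell it from a stimulation effect. It also cannot be repaired afterwards from scores assigned with the setting known, unless the sheets are scored again under masking.

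**Working it through.** No figure in the plan bears on masking, so the first three steps compare the text and the fourth is an illustration.

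**1. Which measures are exposed.**

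| Measure | How recorded or scored | Room for scorer judgement |
|---|---|---|
| Verbal fluency | Paper (12.0) | Accepting or rejecting words |
| D-KEFS CWIT | Paper (12.0); time and errors (3.0) | Error calls; how time is taken is not stated |
| RNGT | Paper (12.0); tone-paced, repetition, cycling and seriation measures (3.0) | Less: indices computed from the digits |
| Quotient | Device algorithm (3.0); exploratory (13.0) | None in scoring; its administration is still unmasked |

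**2. Why rotation does not help.** Write a score as patient effect + period effect + setting effect τ + scoring bias b for that setting. If the three orders repeat over 30 patients, each setting falls 30/3 = 10 times in each of the three positions, so additive period effects cancel from a difference between settings. What remains for theta versus gamma is (τ_theta − τ_gamma) + (b_theta − b_gamma). The bias term has the same index as the effect and stays. The same holds for on versus off.

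**3. Why patient code plus session number is not a mask.** The Section 6.0 example gives patient 1 gamma, theta, off; patient 2 theta, off, gamma; patient 3 off, gamma, theta. If the cycle repeats, patient 8 has the order of patient 2 (8 = 2×3 + 2). With baseline as session 1 (Section 9.0), that patient's session 3 is off. If the code follows enrolment order, those two numbers give the setting without any order list.

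**4. Illustration of size.**

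Inputs from Section 13.0: n = 30; verbal fluency SD 17; planned change 9.4. Assumptions: the fluency unit is words; the net bias between two settings is b = 1, 2 or 3 words; there is no true effect; the test is a two-sided 5% paired t. The plan does not give the SD of a paired difference. It is taken as 17 (the table SD, which equals the paired SD if the within-patient correlation is 0.5) or as 13.

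b as a share of the planned change: 1/9.4 = 11%, 2/9.4 = 21%, 3/9.4 = 32%.

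Noncentrality λ = b√30/SD. False-positive rate = P(|T| > 2.045), with T noncentral t on 29 degrees of freedom.

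| b | λ (SD 17) | Rate | λ (SD 13) | Rate |
|---|---|---|---|---|
| 0 | 0 | 0.050 | 0 | 0.050 |
| 1 | 0.32 | 0.061 | 0.42 | 0.069 |
| 2 | 0.64 | 0.096 | 0.84 | 0.129 |
| 3 | 0.97 | 0.155 | 1.26 | 0.231 |

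As a cross-check on all three tasks with projected sample sizes, the table SDs were used as paired SDs. A bias of 10% of the planned change gives about 6%, 25% gives 11–13%, and 50% gives 30–37%.

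**The case against.** Single-blind is a declared choice in a single-center pilot, not an oversight or a contradiction. That stands: the point is a gap in protection, not an error in the text.

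A reader might infer that the tasks are timed and scored by hand by someone who knows the setting. The documents do not say so. They give paper collection and time-and-error scoring, and are silent on who programs, who tests, who scores and how time is taken. A knowing scorer is permitted by that silence, not stated.

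A reader might also infer that masking the sheets removes the bias, or that it needs no additional people. Neither is supported. Timing, prompting and pacing during the session are untouched by a coded sheet. Returning motor signs may reveal off, and possibly theta, so protection is weakest for aim 1. Staffing is not described, so separating programmer from scorer may or may not be possible within the team.

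The size and direction are also open. The 1 to 3 words are assumed, and the paired SD is not in the plan. For fluency under gamma, a tester aware of the reported decline (Section 1.0) might lean the other way. The two-sided rate is the same for either sign, but the direction of a false finding is not.

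What survives is narrower: scoring that can be done from the sheet can be masked, and the plan does not ask for it.

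**Conclusion.** The concern holds in a limited form. The plan withholds the setting from the patient only and does not keep it from the scorer of the three tasks that carry projected sample sizes. Fluency counts and CWIT error tallies are the most exposed, RNGT indices less so, and Quotient scoring is not open to this bias. Any such bias would follow the setting, survive the rotation and enter both aims.

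Its size is unknown. The rates of about 6%, 10% and 15% (paired SD 17) or 7%, 13% and 23% (paired SD 13) show what an assumed bias of 1, 2 or 3 words would do; they do not estimate what will happen. It would go too far to conclude that the results will be biased or that the scorers are known to be unmasked. The change is worth making before testing starts.

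**What to change.** In Sections 6.0 and 12.0:

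1. Label each score sheet with a random code that reveals neither the setting, the enrolment number nor the session order. Patient code plus session number is not enough.
2. Keep the order list and the code key with the person who reprograms the stimulator. Where the team allows, have the coded sheets scored by a member of the existing study personnel who holds neither. If one person fills all roles, score the coded sheets in a batch in random order, and accept that this is weaker because that person may recall the session.
3. Finalise and lock RNGT, fluency and CWIT error scores before the setting is merged in.
4. State who programs, who tests and who scores, and whether each is masked.
5. Record as limitations that live timing and prompting are not masked by these steps, and that off, and possibly theta, may be inferred from returning motor signs.

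The cost is a small coding and custody task plus a lock-then-merge step. Full separation of programmer and scorer cannot be assumed, because staffing is not described. No stimulation setting, visit or patient procedure changes.

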#### **7.0 STUDY AGENT ADMINISTRATION OR INTERVENTION AND TOXICITY MANAGEMENT PLAN**

During the "on" phase, bilateral monopolar stimulation of the electrode contact associated with the ventral STN will be turned on; testing in the "on" state will be tested at both theta (5-10 Hz) and gamma (100-180 Hz) stimulation. In order to

improve blinding to “on” versus “off” states and increase the uniformity of stimulation parameters, the intensity will be adjusted to 2.5 V for all patients. During the “off” phase, both DBS electrodes will be turned off.

Parkinson’s disease patients routinely have their settings changed to optimize their therapy if they are not having adequate response to their current treatment, especially in their first few programming sessions. Patients also have a controller to turn it off and on. Stimulation is routinely turned off in clinic to check for symptoms, or by the patients, who have a controller. Many patients turn their stimulation off at night or for other reasons. The length of time (45 minutes) and adjustments that we are performing would only be for research. Theta stimulation is not routinely used clinically and would only be for research.

There are no risks of turning the stimulation off or lowering the frequency, but it is possible that during this they will not have the motor benefits of DBS (tremor, bradykinesia may return); however, once normal stimulation is turned back on this will resolve. Patients will be monitored during the testing and can stop participating at any point and we will return their stimulation settings back to baseline.

The CTSI Scientific Committee reviewed this study

### 8.0 ASSESSMENT OF EFFICACY AND SAFETY

Patients will be monitored during the testing. We will ask the patient to inform us if they are feeling uncomfortable and want to stop participating or take a break. If patients want to stop participating, we will return the patients stimulation settings to baseline. Any adverse side effects will be reported to the IRB.

### 9.0 CLINICAL AND LABORATORY EVALUATIONS AND STUDY CALENDAR

Baseline (Session 1)	Session 2	Session 3	Session 4
RNGT (5 minutes)	RNGT (5 minutes)	RNGT (5 minutes)	RNGT (5 minutes)
Verbal Fluency (5 minutes)	Verbal Fluency (5 minutes)	Verbal Fluency (5 minutes)	Verbal Fluency (5 minutes)
D-KEFS CWIT (10 minutes)	D-KEFS CWIT (10 minutes)	D-KEFS CWIT (10 minutes)	D-KEFS CWIT (10 minutes)
Quotient Task (20 minutes)	Quotient Task (20 minutes)	Quotient Task (20 minutes)	Quotient Task (20 minutes)

(All during one day)

### 12.0 DATA COLLECTION AND MONITORING

RNGT, Verbal Fluency, D-KEFS CWIT task results will be de-identified using a key and collected on paper. They will be stored in a locked cupboard in a locked office. MRNs and the key will be kept on a password protected Excel 2016 (Microsoft) spreadsheet on an encrypted and secure computer. No one except the study personnel will have access to the spreadsheets or papers. The behavioral data collection process is built into the Quotient ADHD System, details of which are described on their website (<http://www.quotient-adhd.com>).

Data collected from patients electronic medical records will be coded and kept on a password protected Excel 2016 (Microsoft) spreadsheet on an encrypted and secure computer separate from the key. No one except the study personnel will have access to the spreadsheets or papers.

### 13.0 STATISTICAL CONSIDERATIONS

Based upon our power analyses, our sample sizes for each of the tasks range from 20-29 patients. Therefore, we will enroll 30 patients to detect significant differences in cognitive function for the first phase of the study.

## Power analyses

Study	Projected Sample Size	Mean Result ± SD	Absolute Change (Percent Change)
RNGT	20	43±14	+8.6 (20%)
Delis Kaplan Executive Function	26	9.1±3.3	±1.8 (20%)
Verbal Fluency (preliminary data)	29	47±17	+9.4 (20%)
Quotient	Exploratory		

Non-parametric data analysis will be performed for each of the tasks, including RNGT, D-KEFS CWIT and the Quotient tasks. Each task will be analyzed using within-subjects ANOVA.

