This study first aims to confirm previous findings that suggest improvement in cognitive tasks with STN high frequency DBS. Specifically, improvements have been found on the Paced Visual Serial Addition Task (PVSAT), and the Random Number Generation Test (RNGT), which evaluate attention, concentration, task switching, working memory, cognitive processing speed, and executive function. We will also validate the acute effects of DBS on verbal fluency.

To our knowledge, prior studies have not examined the influence of "on" versus "off" stimulation on impulse control. We also propose to examine impulse control, as increased impulsivity is associated with reduced frontal-striatal connectivity in PD patients. Impulsivity will be measured with the Quotient Test, which has been previously used to assess patients with attention-deficit/hyperactivity disorder.

The second aim of this study is to determine if low frequency (theta) stimulation will improve performance on various cognitive tasks more than high frequency stimulation.

Recent findings that suggest theta stimulation improves executive function compared to gamma stimulation raises the possibility that a mix of stimulation frequencies may be required to optimize motor and neurocognitive benefits. This study will directly compare theta versus gamma stimulation to provide further insight into this intriguing possibility.

PD patients with STN DBS electrodes represent a unique opportunity to study this circuitry in humans. Such studies would increase our understanding of role of the basal ganglia in executive and higher cognitive functioning. Confirmation of a direct influence of STN DBS on cognitive function in our patient population would serve as the basis for additional studies that identify the underlying neurophysiological correlates. Our current study has two specific aims: (1) evaluate the acute effects of high frequency (gamma) STN stimulation on cognitive tasks and (2) compare the outcomes to acute effects of low frequency (theta) STN stimulation.

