## 2.0 OBJECTIVES AND PURPOSE

The first aim of this study is to validate previous neurocognitive changes demonstrated in PD patients with DBS stimulation “on” versus “off” utilizing standard DBS stimulation paradigms. The second aim is to determine if low frequency (theta) stimulation results in improved cognitive performance compared to gamma stimulation. Specifically, we will perform tests that evaluate cognitive processing efficiency, executive function and impulsivity, including the Random Number Generation Test (RNGT), Delis Kaplan Executive Function System (including verbal fluency), Color Word Interference Test (D-KEFS CWIT), and the Quotient Test, respectively. Validation of cognitive improvements at specific stimulation frequencies may lead to identification of stimulation parameters that improve executive function in PD patients. These findings will also serve as the basis for future studies investigating the neurophysiological basis for STN-mediated influences on cognition.

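### The analysis section fixes no test, no contrast for either pairwise aim and no order analysis, and the one-step rotation leaves first-order carry-over unbalanced

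*Combined protocol and SAP*

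**What the plan says.** The analysis text is two adjacent sentences under Power analyses in Section 13.0: "Non-parametric data analysis will be performed for each of the tasks, including RNGT, D-KEFS CWIT and the Quotient tasks", followed by "Each task will be analyzed using within-subjects ANOVA". No test is named, and the levels of the within-subjects factor are not given. In particular, the plan does not say whether the baseline session, which always comes first, is a level. Planned comparisons and multiplicity are not mentioned.

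The aims are pairwise. Section 1.0 sets out to "evaluate the acute effects of high frequency (gamma) STN stimulation on cognitive tasks", which Section 2.0 frames as stimulation on versus off at standard settings. The second aim is to "determine if low frequency (theta) stimulation results in improved cognitive performance compared to gamma stimulation".

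Section 3.0 lists several RNGT measures (repetition, cycling, seriation) and, for each CWIT subtest, a time and error counts. The power table does not say which of these its means and SDs describe.

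On order, Section 3.0 notes that switching stimulation "may induce motor effects that could influence testing performance" and says "we will examine if the order in which settings are applied impacts the results of cognitive testing". Section 6.0 gives the rotation: "patient 1: gamma, theta off; patient 2: theta, off, gamma; patient 3: off, gamma theta". Section 13.0 does not mention order, period or sequence.

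**The concern.** Three things are left open.

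- **Test and contrasts.** The two sentences could describe one rank-based within-subjects analysis, a parametric ANOVA, or a set of paired tests. An overall test across three settings can be significant without saying anything about theta against gamma. Test and score could also be settled after the data are seen.
- **Order.** A promised examination has no defined analysis.
- **Carry-over.** A one-step rotation puts each setting equally often in each position, but whenever a setting is not first it follows the same other setting. If part of one setting's effect persists into the next session, the setting differences absorb it, and a position term does not remove it.

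At stake are a false theta-gamma difference under Aim 2 and a diluted gamma-off difference under Aim 1.

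**Working it through.** **The plan's own figures.** The projected sizes are 20, 26 and 29 (RNGT, D-KEFS, verbal fluency). Alpha and power are not stated. Assuming two-sided 0.05, 80% power and the tabled SD as the SD of the paired difference, n = ((1.96 + 0.84) × SD / change)² gives 21, 27 and 26. The paired-t version gives 23, 29 and 28. Neither matches all three. Independent-groups formulas give 33-71 per arm and do not fit. The sizes look like one paired comparison per task. The point below does not depend on them.

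**Inputs.** N = 30 (Section 13.0), 10 per sequence. Standardised change D from the power table: 8.6/14 = 0.614, 1.8/3.3 = 0.545, 9.4/17 = 0.553. Let s be the SD of the paired difference divided by the tabled SD. It is not stated. With within-patient correlation ρ, s = √(2(1 − ρ)), so ρ = 0.7, 0.5 and 0 give s = 0.77, 1 and 1.41. The main case is s = 1. The residual variance is s²/2.

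**Overall test, if three levels are meant.** For (gamma, theta, off) = (D, D, 0) the squared deviations from the mean sum to (2/3)D². The noncentrality is 30 × (2/3)D² / (s²/2) = 40(D/s)², or 15.1, 11.9 and 12.2 at s = 1. With F on 2 and 58 df, power is 93%, 86% and 87%; over the range of s it is 56-99%. The Aim 2 difference is zero throughout. For (D, D/2, 0) the noncentrality is 30(D/s)². At s = 1 the overall test then has 74-84% power, against 83-91% for gamma minus off as a planned contrast.

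**Choice of test for one contrast.** In simulation (20,000 trials, s = 1), taking the smaller of the paired-t and signed-rank p-values gives 5.9-6.3% type I error. When the true difference is D, the two tests disagree in 2.9-4.4% of trials with normal scores and in 8.3-11.6% at an assumed skewness of 3.7 (0.6-6.4% and 3.0-18.4% over the range of s).

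**Carry-over under the rotation.** Each setting follows baseline in 10 patients, which cancels. In the other 20, theta follows gamma, off follows theta, and gamma follows off. Let a fraction c of the previous setting's effect persist, with theta equal to gamma (both D) and off zero. The mean carry-over is then (20/30)cD for theta, (20/30)cD for off and 0 for gamma. So theta minus gamma is biased by +(2/3)cD, and gamma minus off is reduced by the same amount. With a position term the SE of a contrast is s/√30, so the Aim 2 noncentrality is (2/3)cD√30/s. For RNGT at c = 0.50 and s = 1 it is 0.333 × 0.614 × 5.48 = 1.12.

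| c | Bias, RNGT points | Aim 2 type I error, s = 1 | Aim 2 type I error, s = 0.77 to 1.41 | Gamma-minus-off power, s = 1 |
|---|---|---|---|---|
| 0 | 0 | 5% | 5% | 83-91% |
| 0.10 | 0.6 | about 5% | 5-6% | 78-87% |
| 0.25 | 1.4 | about 8% | 6-11% | 69-79% |
| 0.50 | 2.9 | 16-19% | 11-30% | 49-59% |

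Over the range of s, gamma-minus-off power is about 55-99% at c = 0 and 28-81% at c = 0.50.

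**Fitting carry-over.** With patient, setting, position and carry-over in the model, the three-sequence design has full rank (36 of 36). The contrast variance rises from 0.0667 to 0.3333 residual variances: ×5, or SE × 2.24.

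**Adding the three reversed sequences (5 patients each).** Each setting now follows each other setting in 10 patients. Mean carry-over is (10/30)cD for gamma, (10/30)cD for theta and (20/30)cD for off. The Aim 2 bias is zero when theta equals gamma, and the loss in gamma minus off halves to (1/3)cD. With a carry-over term the variance is 0.0833: ×1.25, or SE × 1.12.

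**The case against.** A reader might infer that the analysis must be an overall test whichever sentence is followed. The text does not say so. Non-parametric analysis could mean paired signed-rank tests, and a two-level within-subjects ANOVA for each aim is a paired t-test. The power table gives one change per task, and its sizes look like a paired comparison. The 86-93% figure therefore holds only if a three-level test is intended. A Friedman-type analysis would also reconcile the two sentences, so they are unclear rather than contradictory.

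A reader might also infer from the calendar (4 × 40 = 160 minutes) and "Duration of testing will be approximately three hours" that only about 20 minutes remain for changing settings. The three hours describe testing and need not include changes or breaks, so nothing here rests on that.

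It can fairly be said that carry-over is hypothetical, that Section 3.0 promises only to examine order, that the aims already name both comparisons, and that for one contrast the choice between t and signed-rank matters little. All of that stands. It limits the size of the point but supplies no test, contrast or order analysis. The gap is not a redaction effect, because the contents list shows no other statistics section.

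**Conclusion.** The concern holds in this form. Section 13.0 does not state the test, factor levels or contrasts for two pairwise aims, and it has no analysis for the order examination promised in Section 3.0. The rotation in Section 6.0 balances position but not first-order carry-over.

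The textual gaps need no assumption. The sizes do: 30 patients in equal sequences, the tabled changes, an SD of the difference between 0.77 and 1.41 times the tabled SD, and, for carry-over, a c that the documents do not give. At c = 0.10 the effect on Aim 2 is slight; at c = 0.50 type I error is about 11-30%.

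The documents do not show that carry-over occurs, and the point does not invalidate the design. Leaving out the position term would not bias setting differences under additive session drift when all sessions are completed; it would make the tests conservative. For a single-centre pilot with Quotient exploratory, this should be fixed before analysis.

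**What to change.** 1. Replace the two analysis sentences with one analysis of one named score per task, and say whether that score is the one behind the tabled mean and SD. Use a within-patient model with setting (gamma, theta, off) and session position (2, 3, 4). State that the baseline session is not a setting level. Plan two contrasts: gamma minus off (Aim 1) and theta minus gamma (Aim 2). Use a signed-rank test of the same contrasts as sensitivity analysis, or as primary if the sponsor prefers rank methods. State how multiplicity over the two contrasts and the tasks is handled.
2. Report the position effect as part of the order examination, and say that it does not remove carry-over.
3. For patients not yet enrolled, also use the reversed sequences (off-theta-gamma, gamma-off-theta, theta-gamma-off), which with 30 patients gives 5 per sequence.

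**Cost.** Wording, 2 of 58 error degrees of freedom, and a changed allocation list, with no added patients or sessions. At s = 1 and without drift, gamma-minus-off power is 83-91% with or without the position term. Signed-rank loses 1-2 points of power with normal scores and gains 4-5 at skewness 1.75 and 8-11 at skewness 3.7. If the sponsor chose Bonferroni over the two contrasts (0.025 each), paired-t power at 30 patients and s = 1 would fall from 90.2%, 82.3% and 83.3% to 83.5%, 73.1% and 74.4% (RNGT, D-KEFS, verbal fluency).
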